### Study Design: RCT

Participants will be randomized to two groups: Group A or Group B; each will receive messages over 4 weeks that will consist of blogshots for different CWC recommendations [18]. Participants who complete the baseline questionnaire will receive one blogshot via email every week for three weeks and the fourth week will include a summary of all three blogshots. This will be automated through the Nooro platform. Through the Nooro platform we will monitor if participants have opened the email and viewed the blogshot. If an email has not been opened for 3 days, a reminder email will be sent. At the end of the four-week campaign, participants will be asked to complete a follow-up questionnaire after the intervention at week 5 and then at three and six months post-intervention. The group topics will be:

Group A;

- *Don't routinely do a throat swab when children present with a sore throat if they have a cough, rhinitis, or hoarseness;*
- *Don't recommend the use of cough and cold remedies in children under six years of age;*
- *Don't use antibiotics for acute asthma exacerbations without clear signs of bacterial infection.*

[figure not shown]
Group B;

- *Don't routinely use antibiotics in children with uncomplicated sore throats;*
- *Don't prescribe antibiotics in adults with bronchitis/asthma and children with bronchiolitis;*
- *Don't use antibiotics in adults and children with uncomplicated acute otitis media.*

**Randomization:** Blocked randomization with randomly chosen block sizes will be used to ensure equal distribution of participants to each study arm. The blocked randomization sequence will be computer generated. Parents will be randomized to either group A or group B when completing the demographic and baseline questionnaire on the electronic platform.

**Sample Size:** We will aim to recruit 180 parents (90 participants per group). This is based on assuming a 10% difference between groups in knowledge scores and a standard deviation of 2.0

with 80% power. This would require 64 participants per group and we have increased this number by 25% to allow for dropouts.

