**Figure 1: Study Design**

**Blogshot Development:** Six blogshots were developed with the assistance of a graphic designer. Members of the P-PAG provided feedback on the language, design and content of the blogshots.

**Online Questionnaire Development:** The research team developed four questionnaires (baseline and 3 follow-up questionnaires). The questionnaires consist of multiple choice knowledge questions based on the information presented in the blogshots, questions about participant’s intentions for managing common acute childhood conditions and actions participants took if their child developed symptoms of one of the conditions from the blogshot during the duration of the study. A series of 7 questions about the usability of the blogshots will be included in the questionnaire as well.

The questionnaire is designed and housed in the Nooro platform (<https://nooro.com>). An overview of each question category is listed below:

**Baseline Questions:** Four baseline questions will be included about parent’s experience with the common acute childhood conditions included in the blogshots as well as number of times they went to the emergency department or received a prescription for antibiotics for their child. A question about information seeking is also included. **These questions are asked at baseline.**

**Knowledge Questions:** Each topic will have three “core” knowledge questions that will be included at baseline and all three follow-up questionnaires. An additional knowledge question will be included for each topic in which a participant received a blogshot. For example, group A will

receive one extra question for the sore throat swab, cough and cold medication and bronchiolitis topic and group B will receive an extra question on acute otitis media, asthma exacerbations and sore throat. **These questions are asked at baseline, follow-up 1, follow-up 2 and follow-up 3.**

**Expectation Questions:** Each blogshot topic will have 1 expectation question that asks parents about their expectations from a healthcare provider on the management and treatment of each condition. **These questions are asked at baseline and follow-up 1.**

**Intention Questions:** Each blogshot topic will have one intention question that asks parents about their intentions on the management and treatment of each condition. **These questions are asked at baseline and follow-up 1.**

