## Outcomes

The will be knowledge immediately after the campaign; we will compare change from baseline between groups (i.e. average change in knowledge scores specific to CWC recommendations, expecting that knowledge will improve with respect to the content received). Secondary outcomes will be intentions, expectations of care and usability of the blogshots. We will explore if outcomes were influenced by whether a child had one of the conditions (and identify actual behaviour). All outcomes will be assessed both quantitatively through questionnaire responses and qualitatively through the semi-structured interviews.

The outcomes will focus on the following 5 domains:

**Knowledge:** Knowledge will be assessed by comparing participant's scores on baseline questionnaire to follow-up questionnaire 1 (knowledge change) and comparing scores to follow-up questionnaires 2 and 3 (knowledge retention).

**Expectations:** Participants will be asked questions about their expectations of healthcare professionals at baseline and follow-up 1 questionnaires. We will compare at baseline and follow up to assess if the blogshots led to a change in expectations of healthcare professionals.

**Intentions:** Participants will be asked questions about their intentions at baseline and follow-up 1 when they seek healthcare i.e. are they seeking antibiotics from a healthcare professional.

**Actions:** Participants will be asked about actions they took during the course of the study in follow-up questionnaires 2 and 3. For example if their child had symptoms related to information in the blogshot and the actions they took i.e. went to a physician, filled a prescription for antibiotics, etc.

**Usability of the blogshots:** Participants will complete usability questions about the blogshots focusing on topics such as if the blogshots increase knowledge, aid in decision-making and are relevant to parents. This will be completed at follow-up 1.

The semi-structured interviews will include questions on all 5 of these domains to clarify, expand on and provide to context to the questionnaire responses.

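### Each extra knowledge item goes to one arm only, so 6 of 24 items cannot enter the between-arm comparison and 9 rather than 12 comparable items remain per topic set

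*Combined protocol and SAP*

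**What the plan says.** Under Online Questionnaire Development, the Knowledge Questions paragraph sets a common core: "Each topic will have three “core” knowledge questions that will be included at baseline and all three follow-up questionnaires". It then adds an arm-dependent part: "An additional knowledge question will be included for each topic in which a participant received a blogshot". The paragraph closes with the timing for the category, "These questions are asked at baseline, follow-up 1, follow-up 2 and follow-up 3", and makes no exception for the extra items. There are six topics, three per group ("Six blogshots were developed with the assistance of a graphic designer").

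The same paragraph gives an example. For the first group its wording is "receive one extra question for the sore throat swab, cough and cold medication and bronchiolitis topic". By the same example, the other group's extra items concern sore throat, asthma exacerbations and otitis media. The topic lists under Study Design: RCT differ on two of these. They place the asthma message ("Don't use antibiotics for acute asthma exacerbations without clear signs of bacterial infection") in group A and the bronchiolitis message in group B.

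Randomisation takes place while the parent completes the baseline questionnaire, so arm-specific items at baseline are feasible. For the primary outcome, knowledge straight after the campaign, the Outcomes section says "we will compare change from baseline between groups". Neither Outcomes nor Plan for Data Analysis says whether the extra items count in the knowledge score.

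**The concern.** Each arm serves as the control for the topics taught to the other arm. An item can inform that contrast only if both arms answer it. An item answered by one arm supports at most an uncontrolled before-after change, which mixes the blogshot's effect with retest gain and anything learned elsewhere. The plan writes and administers six such items and gives no reason for keeping them arm-specific.

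There is a second, smaller issue. Under the general rule, parents are asked four questions on each topic they are taught and three on each topic they are not. The amount of questioning then varies with the allocation. Limiting the score to the core items deals with the missing control answers but leaves this imbalance in place.

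**Working it through.** **Item count** (inputs from Knowledge Questions and Blogshot Development)

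- Core items: 6 topics × 3 = 18, asked of everyone.
- Extra items: 6 topics × 1 = 6, each asked of one arm.
- Pool: 18 + 6 = 24. Each parent answers 18 + 3 = 21.
- Items answered by one arm only: 6/24 = 25% of the pool. For any one parent, 3/21 = 14.3% of the items are not put to the other arm.
- Comparable items per three-topic set: 3 × 3 = 9. With common extras it would be 3 × 4 = 12.

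**Who is asked what**

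| Reading | Taught arm, per set | Other arm, per set |
|---|---|---|
| General rule | 4 + 4 + 4 = 12 | 3 + 3 + 3 = 9 |
| Literal example | 4 + 4 + 3 = 11 | 3 + 3 + 4 = 10 |

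Under the literal example, four extras go to the taught arm and two (asthma, bronchiolitis) to the untaught arm. The additional questioning then favours the taught arm on four topics and the other arm on two. On both readings 6 of 24 items have one-arm answers.

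**The plan's own sample size.** Study Design: RCT gives a 10% difference, SD 2.0, 80% power and 64 per group. Reading 10% as 1.0 point, the standardised difference is 1.0/2.0 = 0.5. A two-sided 5% t-test then needs 63.8, rounded up to 64, so the figure reproduces. That reading implies a 10-point scale, which the documents do not state. Placing 0.5 SD on a 9-item set is therefore an assumption.

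**Gain from 12 common items.** Let r be the reliability of the 9-item score that is analysed. Spearman-Brown with k = 12/9 gives R = k·r / (1 + (k − 1)·r), and the standardised difference is multiplied by √(R/r). This takes the extra items to be as good as the core items and to respond to the blogshot in the same way.

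| r (assumed) | R | √(R/r) | d = 0.5 × √(R/r) | Power, 64 per arm |
|---|---|---|---|---|
| 0.4 | 0.471 | 1.085 | 0.542 | 86.1% |
| 0.5 | 0.571 | 1.069 | 0.535 | 85.1% |
| 0.6 | 0.667 | 1.054 | 0.527 | 84.1% |
| 0.7 | 0.757 | 1.040 | 0.520 | 83.1% |

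The reference is 80.1% at d = 0.5. The equivalent saving in parents is 1 − r/R: 15% at r = 0.4 (1 − 0.4/0.471) and 7.5% at r = 0.7 (1 − 0.7/0.757). At the full 90 per arm with no dropout, the same calculation takes power from 91.6% to between 93.4% and 95.1%.

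**The case against.** The strongest reply is that the primary comparison is already sound. The core items are asked of both arms at every questionnaire, and 9 matched items per topic set support a randomised comparison of change. The extras could serve as within-arm description. This stands. A reader might infer that the two arms sit different tests and that the primary contrast is therefore biased. The documents do not support that: bias from this source would need the extras to enter the score, and the plan is silent on whether they do.

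A reader might also infer that every taught topic gets a third more questioning (4 items against 3) and that this contaminates the blogshot effect. That figure holds only under the general rule; under the literal example it is 11 against 10 per set, and it reverses for two topics. Before the primary assessment the difference is at most one multiple-choice item per topic, asked once. Both arms have by then also answered three core items, one expectation item and one intention item on each topic. No answer feedback is described. A testing effect is possible, but the documents give no size for it and it is probably small.

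The timing is also less than certain. The extra-item rule refers to blogshots already received, and at baseline none has been sent. The closing sentence on timing covers the whole category, so baseline use is the more natural reading. If the extras came only at follow-up, they would lack a baseline as well as a control, and the questionnaires would still differ between arms.

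Finally, the power gain rests on assumed reliability. The primary outcome is a change score, and the documents report no reliability for either single-visit or change scores. This stands, so the gain is a range under assumptions.

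**Conclusion.** The point holds as a matter of efficiency and comparability. A quarter of the item pool (6 of 24) has answers from one arm only, whichever of the protocol's two descriptions is followed, and cannot enter the between-group change. The 9 core items per set still give a valid randomised contrast.

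The forgone precision is modest: about 3 to 6 percentage points of power at 64 per arm. This depends on an assumed 9-item reliability of 0.4 to 0.7, extra items of similar quality, and a 0.5 SD difference on the 9-item set. The unequal questioning is avoidable; its effect is unknown, and its direction by topic depends on how the asthma and bronchiolitis conflict is resolved. This is a cheap improvement, not a defect that invalidates the plan.

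**What to change.** Ask all 24 knowledge items of both arms at baseline and at all three follow-ups, and state that the between-group comparison uses the 12 items of each topic set. Every item then has a control answer and questioning is equal across arms.

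If questionnaire length is a concern, drop the six extras. That also equalises questioning but gives up the precision gain. Keeping them arm-specific has neither benefit.

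Reconcile the example under Knowledge Questions with the group lists under Study Design: RCT for the asthma and bronchiolitis topics. If any extra stays arm-specific, state whether it is asked at baseline and whether it counts in the knowledge score.

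Cost: three more multiple-choice items per questionnaire (21 to 24) and an edit on the questionnaire platform.

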### Study Design: Qualitative Interviews

Qualitative interviews will be conducted with a sub-set of participants (approx. 30). This sample size is based on qualitative research methodology for performing on-one-one interviews [16, 17]. Participants will be invited to participate in the semi-structured interview while completing the week 5 follow-up questionnaire 1. Participants who are interested in participating in an interview will leave their first name and email address and will be contacted by the project coordinator to schedule an interview.

The purpose of the interviews is to further understand and contextualize participant's responses and perspectives on the efficacy of the blogshots to increase knowledge, influence intended behavior and expectations on the common acute childhood conditions [18]. The honeycomb model of user experience was used to guide the development of the interview questions [13, 19]. We will also explore parent preferences regarding format and mode of information delivery and study recruitment, which could inform future campaigns and evaluations

**Incentives:** Participants will be compensated a \$10 CAD electronic gift card per questionnaire completed (not including baseline) to a maximum of a \$30 CAD electronic gift card for completing all three follow-up questionnaires. For the qualitative component, we will compensate participants an additional \$25 CAD electronic gift card for participation in the interview. This incentive will come in the form of an electronic CAD gift card to the participant.

## Data Collection

The following data will be collected over the course of the study:

1. **Baseline questionnaire:** Participants will complete a pre-intervention questionnaire that includes demographics, knowledge about antibiotic use and common acute childhood conditions, intentions about whether they would seek healthcare for their child for a

common childhood condition and their expectations on management by healthcare providers.

2. **Follow-up questionnaire 1 (5 weeks after baseline):** Participants will re-do all knowledge, intentions and expectation questions as well as provide feedback on the blogshot design.
3. **Follow-up questionnaire 2 (3 months after baseline):** Participants will re-do knowledge questions (knowledge retention). They will also be asked action questions about whether their child experienced any of the conditions and what actions they took (e.g. sought healthcare services, over the counter medications, filled prescriptions).
4. **Follow-up questionnaire 3 (6 months after baseline):** Participants will re-do knowledge questions and action questions.
5. **Qualitative Interviews (post intervention):** Interviews will be conducted over zoom video conferencing software and recorded and transcribed using a third-party transcriptionist.

## Outcomes

The will be knowledge immediately after the campaign; we will compare change from baseline between groups (i.e. average change in knowledge scores specific to CWC recommendations, expecting that knowledge will improve with respect to the content received). Secondary outcomes will be intentions, expectations of care and usability of the blogshots. We will explore if outcomes were influenced by whether a child had one of the conditions (and identify actual behaviour). All outcomes will be assessed both quantitatively through questionnaire responses and qualitatively through the semi-structured interviews.

The outcomes will focus on the following 5 domains:

**Knowledge:** Knowledge will be assessed by comparing participant's scores on baseline questionnaire to follow-up questionnaire 1 (knowledge change) and comparing scores to follow-up questionnaires 2 and 3 (knowledge retention).

**Expectations:** Participants will be asked questions about their expectations of healthcare professionals at baseline and follow-up 1 questionnaires. We will compare at baseline and follow up to assess if the blogshots led to a change in expectations of healthcare professionals.

**Intentions:** Participants will be asked questions about their intentions at baseline and follow-up 1 when they seek healthcare i.e. are they seeking antibiotics from a healthcare professional.

**Actions:** Participants will be asked about actions they took during the course of the study in follow-up questionnaires 2 and 3. For example if their child had symptoms related to information in the blogshot and the actions they took i.e. went to a physician, filled a prescription for antibiotics, etc.

**Usability of the blogshots:** Participants will complete usability questions about the blogshots focusing on topics such as if the blogshots increase knowledge, aid in decision-making and are relevant to parents. This will be completed at follow-up 1.

The semi-structured interviews will include questions on all 5 of these domains to clarify, expand on and provide to context to the questionnaire responses.

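### The primary knowledge score is not tied to items both arms can be compared on: some permitted scores cancel a real effect, and comparing each topic set gives two tests with no success rule

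*Combined protocol and SAP*

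**What the plan says.** - **Arms.** In Study Design: RCT, both groups are active: "each will receive messages over 4 weeks that will consist of blogshots for different CWC recommendations". Three recommendations are listed for each. No arm goes without blogshots.
- **Items.** The Knowledge Questions paragraph gives every topic three core "knowledge questions that will be included at baseline and all three follow-up questionnaires". It then adds: "An additional knowledge question will be included for each topic in which a participant received a blogshot".
- **Primary outcome.** Outcomes compares change from baseline, right after the campaign, "between groups (i.e. average change in knowledge scores specific to CWC recommendations, expecting that knowledge will improve with respect to the content received". The knowledge domain in the same section repeats the baseline to follow-up 1 comparison without naming items, scoring or group.
- **Analysis.** Plan for Data Analysis offers an independent t-test or chi-squared test between groups and paired tests over time, with two-sided 95% intervals and a 5% threshold. None is tied to a particular score.
- **Sample size.** The plan has 64 per group for 80% power, "assuming a 10% difference between groups in knowledge scores and a standard deviation of 2.0", raised to 90 per group for dropout.
- **Topic assignment.** Study Design: RCT gives Group A the asthma topic ("use antibiotics for acute asthma exacerbations without clear signs of bacterial infection") and Group B the bronchiolitis topic ("prescribe antibiotics in adults with bronchitis/asthma and children with bronchiolitis"). The example under Knowledge Questions gives the extra bronchiolitis question to A and the extra asthma question to B.

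**The concern.** In a design where each arm serves as the other's control, the randomised comparison is informative only if both arms are scored on the same topic-specific items. A between-group t-test on change in knowledge scores does not secure that. Depending on the items chosen, the same data could show a clear effect, an expected difference of nil, or two results that disagree.

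With no pre-stated score or rule, the choice could be made after the results are known. The objective, whether blogshots raise parents' knowledge, would then rest on that choice rather than on the randomisation.

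**Working it through.** **Inputs.** From the protocol: SD 2.0, 80% power, 64 evaluable and 90 recruited per group, two-sided 5%, six topics (three per arm), three core questions per topic, one extra question per topic received. Assumed, because the documents are silent: one point per item, and r, the within-parent correlation between changes on the two topic sets (range -0.2 to 0.5). Power is from the two-sample t-test. SD 2.0 is taken as the SD of change unless stated.

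**1. The plan's own figure.** With a 1.0-point difference, d = 1.0/2.0 = 0.5. The t-test then needs 63.8, so 64 per group, with power 80.1%. The figure reproduces, but only if 10% means 1.0 point.

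**2. Item counts.** Core items per topic set: 3 × 3 = 9. Own-topic items with extras: 9 + 3 = 12. All core items: 18. All items answered: 18 + 3 = 21. At one point per item, 10% is:

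| Items | 10% in points | n per arm for 80% power |
|---|---|---|
| 9 | 0.9 | 79 |
| 12 | 1.2 | 45 |
| 18 | 1.8 | 21 |
| 21 | 2.1 | 16 |

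None gives 1.0 point. Only the 9-item set is a same-item comparison of one topic set; at 64 per arm its power is 71%.

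**3. Scores that cancel.** Let the blogshots add δ to the topics received and nothing to the others.
- Total over 18 core items: Group A gains δ + 0 and Group B gains 0 + δ. The difference is δ - δ = 0.
- Own-content score: A gains δ on A topics, B gains δ on B topics. The difference is again 0.
- Extra questions: as the text reads, only the arm that received the topic answers them, so they have no comparator.

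**4. Two same-item comparisons.** Each is valid, with expected difference δ.
- Either counts: 1 - 0.95² = 9.75% if independent (about 9.0% at r = 0.5).
- Both must succeed, 64 per arm: 0.801² = 64% at 1.0 point (61% to 66% over the range of r); 0.714² = 51% at 0.9 point (46% to 54%).
- Bonferroni, 2.5% each, 64 per arm: 71% per set at 1.0 point, 61% at 0.9.

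**5. One contrast.** Per parent, D = change on A-topic core items minus change on B-topic core items. Mean D shifts by +δ in A and -δ in B, so the arms differ by 2δ. SD of D = 2.0 × √(2(1 - r)), which is 2.83 at r = 0. Baseline adjustment is ignored here.
- At 1.0 point: d = 2.0/2.83 = 0.707, power 98% at 64 per arm.
- At 0.9 point: d = 1.8/2.83 = 0.636, power 95%; 80% power needs 40 per arm (48 at r = -0.2).
- If only one set works, 1.0 point, r = 0: d = 1.0/2.83 = 0.354, power 51%.

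**6. Which SD.** If 2.0 is the SD at one time point and baseline correlates ρ with follow-up, the SD of change is 2.0 × √(2(1 - ρ)). For ρ = 0.3, 0.5 and 0.7 this is 2.37, 2.00 and 1.55, and same-item power at 1.0 point and 64 per arm is 66%, 80% and 95%.

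**The case against.** The strongest defence is that Outcomes states one outcome and one comparison, and that its reference to the content received leans towards comparing the same topic items across arms. That reading is fair, and it is a valid analysis. It still yields one comparison per topic set, and nothing says how the two are combined. It is also only a leaning: an all-item total is an equally plain reading of a change in knowledge scores.

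Four stronger readings are tempting and are not supported:
- **That the trial will use a cancelling score, or will run two uncorrected tests.** The text commits to neither. The 9.75% and 64% apply only if two topic-set tests are run.
- **That the item sets cannot be named.** The lists in Study Design: RCT allow a provisional naming of the core sets. The conflicting text is an example about the extra questions only and may be a drafting slip, though it must be reconciled.
- **That a benefit shared by both arms would go unseen.** The paired baseline to follow-up tests could show it, but without a randomised control.
- **That a size can be put on spill-over between topics.** Sore throat features in both lists (a throat-swab topic in A, "routinely use antibiotics in children with uncomplicated sore throats" in B), and asthma is in A's list and in the wording of a B topic. Dilution is plausible, but the documents give no basis for a fraction, so they do not show that 90 per arm is enough, or too few, once it is allowed for.

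Figure 1 and the questionnaires are not reproduced, so scoring may be set out there. The claim is only that it is absent from the supplied text.

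**Conclusion.** The point stands and should be settled before any outcome data are examined. The plan names a comparison, a time point and a threshold, but not the items, the score range or the rule that turns topic-set results into one conclusion. This is more than missing detail, because two scores the wording permits have an expected between-arm difference near zero when both arms gain equally.

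If topic sets are compared separately, the cost is an error of up to 9.75% or power of about 64% against the stated 80%, depending on the rule. Those figures assume independent tests and, for the power, 64 evaluable per arm, 1.0 point and SD of change 2.0. The mismatch between 10% and 1.0 point rests on one point per item. The cancellation needs only equal gains and no carry-over to the other arm's topics.

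**What to change.** 1. Reconcile the asthma and bronchiolitis assignment between the topic lists in Study Design: RCT and the extra-question example under Knowledge Questions.
2. Define the primary endpoint on the shared core items only, leaving out the extra questions. Per parent, take D at follow-up 1 as the change on A-topic core items minus the change on B-topic core items. Compare mean D between arms in one two-sided 5% test adjusted for both baseline sub-scores. Half the difference is the average effect per topic set. Report the A-topic and B-topic between-arm differences with 95% intervals as supportive.
3. State the score range, the 10% difference in points and whether 2.0 is the SD of change, then restate the power on that score.

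If claims for each topic set are wanted instead, pre-specify two same-item tests with a stated rule and restate the power. For 80% power per set, Bonferroni needs 78 evaluable per arm at 1.0 point and 96 at 0.9. For 80% joint power with independent tests, requiring both needs 84 and 103. The 0.9-point figures exceed the 90 recruited.

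**Cost.** The contrast needs new wording in the outcome, sample-size and analysis text. It needs no new data or visits, since both arms already answer the core items at baseline and follow-up 1. Without spill-over, its 40 to 48 evaluable per arm at 0.9 point fit within the planned 90, even after the plan's 25% dropout (0.75 × 90 = 67.5). The downside is that it averages over both sets: power is about 51% at 1.0 point and r = 0 if only one set works. Overlap on sore throat and asthma may dilute it, and no scoring rule removes that.
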